13.2 Statistical Monitoring Plan

Safety and efficacy data will be periodically assessed by the DSMB. Safety and efficacy data will be periodically assessed by the DSMB. For ethical reasons, an interim examination of key safety and endpoint data will be performed at regular intervals during the course of the trial. The interim monitoring will also involve a review of the control arm event rates, patient recruitment, compliance with the study protocol, status of data collection, and other factors that reflect the overall progress and integrity of the study. An NHLBI-appointed DSMB will carefully and confidentially review the results of the interim analyses and status reports. If protocol modifications are warranted, close consultation among the DSMB, the NHLBI staff, and the study leadership will be required. A separate DSMB charter outlining the operating guidelines for the committee and the protocol for evaluation of data will be created prior to study enrollment and agreed upon during the initial meeting of the DSMB.

It is anticipated that the DSMB will meet at 6-month intervals to review the accumulating data. The DCRI will create regular reports to track patient enrollment reports, rates of compliance with the assigned testing strategy, and frequency of protocol violations. Prior to each meeting, the data coordinating center will conduct any requested statistical analyses and prepare a summary report along with the following information: patient enrollment reports, rates of compliance with the assigned testing strategy, frequency of protocol violations, and description of SAEs (statistical comparisons of the randomized arms with respect to these SAEs will use chi-square or other appropriate 2-sample methods).

There will be one planned interim review for efficacy. The efficacy review will focus on the composite endpoint of respiratory hospitalization or all-cause death and should occur once 300 enrolled subjects have been followed for 12 months. The Lan-DeMets alpha spending function with O'Brien-Fleming type boundaries will be used for the interim analysis.

13.3 Site Training Requirements

Clinical sites participating in this study will be trained in the following aspects of the study including a protocol overview covering:

- Good Clinical Practice (GCP) overview
- Inclusion / exclusions
- Protocol activities
- Telephone contact methodology
- SAE reporting expectations
- Blood draw requirements
- Sample processing, storage, and shipping
- Electronic data capture
- Accessing the EDC
- Data entry requirements and scheduling expectations
- Query resolution procedures
- Uploading documentation for outcome event classification

Concomitant Medication Review	X										
Concomitant Medication Update			X			X	X	X	X	X	X

Complete Blood Count (CBC)	X (if not available in last 90 days)			X ³	X ³		X ³		X ³		
Chemistry panel w/liver function tests	X (if not available in last 90 days)			X ³	X ³		X ³		X ³		
Electrolytes only		X ²									
Genotype	X										
Gene expression	X						X		X		
Buccal Swab, Fecal samples	X						X		X		
Patient Reported Outcomes Questionnaires ¹	X						X		X		
Clinical Events			X			X	X	X	X	X	X
Mortality			X			X	X	X	X	X	X
Hospitalization			X			X	X	X	X	X	X
Resp. infection			X			X	X	X	X	X	X

1. Patient reported questionnaires include: UCSD-SoBQ, Fatigue Severity Scale, Leicester Cough, EQ-5D, SF-12, ICECAP-O
2. For subjects receiving co-trimoxazole, a blood sample to document electrolytes will be drawn at week 1, Visit 1A.
3. For subjects assigned to the antimicrobial therapy arm, a blood sample to document complete blood count, liver function tests, and chemistry panel, will be drawn at 3 months, 6 months, 12 months, and 24 months to be obtained at Visit 2A, Visit 2B, Visit 4, and Visit 6, respectively.

16. APPENDIX B – CleanUP-IPF Laboratory Schedule

Antimicrobial Arm (Co-trimoxazole and Doxycycline Arms)

	CBC	Electrolytes	Chemistry plus liver function tests	Gene expression	Genotype	Buccal sample	Fecal sample	Approx. total Blood Amount
Baseline	x		x	x	x	x	x	28.5 ml
Week 1		x*						6 ml
3 month	x		x					8.5 ml
6 month	x		x					8.5 ml
12 month	x		x	x		x	x	18.5 ml
24 month	x		x	x		x	x	18.5 ml
*only in co-trimoxazole treated patients								88.5 ml

Standard of Care Arm

	CBC	Chemistry plus liver function tests	Gene expression	Genotype	Buccal sample	Fecal sample	Approx. total Blood Amount
Baseline	x	x	x	x	x	x	28.5 ml
12 month			x		x	x	10 ml
24 month			x		x	x	10 ml
							48.5 ml

Safety Labs

Complete Blood Count (CBC): WBC, RBC, hemoglobin, hematocrit, mean corpuscular volume (MCV), Platelets, mean platelet volume (MPV)

Electrolytes: Sodium, Potassium, Chloride, Carbon Dioxide (CO₂)

Chemistry: Sodium, Potassium, Chloride, Carbon Dioxide (CO₂), Urea Nitrogen (BUN) and Creatinine

Liver Function Studies: Alkaline Phosphatase, Total Bilirubin, Direct bilirubin, Aspartate Aminotransferase (AST), and Alanine Aminotransferase (ALT)

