5. TREATMENT INTERVENTIONS

This will be an unblinded, randomized clinical trial comparing the following treatment strategies

- Standard care
- Standard care + oral antimicrobial therapy

Patients randomized to receive antimicrobial therapy will receive a prescription drug voucher for the medication (and folic acid if given co-trimoxazole) during the enrollment visit. To minimize risk to the participating subject and to maximize a positive outcome we have created an algorithm for antimicrobial therapy that encourages use of co-trimoxazole but allows doxycycline use.

[figure not shown]
Figure 1 illustrates the proposed antimicrobial therapy algorithm. Contraindications to co-trimoxazole at enrollment include:

- allergy to sulfa products or trimethoprim
- renal insufficiency (GFR < 30 mL/min, defined as estimated from the blood urea nitrogen and creatinine)
- hyperkalemic (potassium > 5 mEq/L)
- concomitantly taking an ACEI, ARB, potassium sparing diuretic, dofetilide, methotrexate, azathioprine, mycophenolate mofetil, cyclophosphamide
- Other contraindication to co-trimoxazole in the investigator's opinion

Subjects meeting any of the above and randomized to antibiotic therapy will take doxycycline instead. Subjects on vitamin A or retinoids will need to stop these medications if randomized to doxycycline.

Co-trimoxazole intolerance is defined by the investigator. Mild intolerance (e.g. nausea, abdominal pain, headaches, anorexia) may require a dose adjustment to half dose. Moderate intolerance (e.g. decreased leukocytes, mild increase in potassium) require a dose adjustment or a switch to doxycycline at the investigator's discretion. A significant intolerance (e.g. leukopenia, hyperkalemia, decrease in GFR by more than 50% or to less than 30 ml/min, rash) requires stopping the co-trimoxazole and providing medical treatment as appropriate. Doxycycline should be started when medically appropriate in the opinion of the investigator after moderate or significant intolerance. All dose adjustments will be at the discretion of the treating physician(s) with the medical monitor available for consultation if needed. Dosing adjustments, and/or switching of co-trimoxazole to doxycycline, will be documented within the eCRFs, as well as the reason for the adjustment.

Figure 1

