8.1 One (1) week lab (Co-trimoxazole assigned subjects ONLY)

Approximately 1 week (visit window of 1 week +/- 3 days) after enrollment (and the beginning of administration of drug), subjects assigned to the antimicrobial therapy arm will return to the enrolling site or a local laboratory for the following:

- Blood drawn for electrolytes (**Described in Appendix B**)

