8.2 One (1) month phone contact

Approximately 1 month (visit window of 1 month +/- 7 days) after enrollment, all subjects will be contacted by the site coordinator to document the following:

- Any issues related to drug assignment
- Vital status assessment
- Medication adherence
- Hospitalization and respiratory infection assessment

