8.3 Three (3) month lab for antimicrobial assigned subjects ONLY

Approximately 3 months (visit window of 3 months +/- 7 days) after enrollment, subjects assigned to the antimicrobial therapy arm will return to the enrolling site or a local laboratory for the following:

- Blood draw for the following safety labs (**Described in Appendix B**):
 - Chemistry panel and liver function tests– defined as minimum of sodium, potassium, chloride, bicarbonate, BUN, and creatinine, total bilirubin, direct bilirubin, alkaline phosphatase, ALT, and AST
 - Complete blood count (CBC)

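### Section 5 stops co-trimoxazole for a fall in GFR, but the protocol schedules no GFR between enrollment and month 3 because the week-1 draw omits BUN and creatinine

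*Protocol*

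**What the plan says.** Protocol Section 5 uses GFR in two places. At enrollment, a contraindication to co-trimoxazole is "renal insufficiency (GFR < 30 mL/min, defined as estimated from the blood urea nitrogen and creatinine"). During treatment, the examples of significant intolerance include a "decrease in GFR by more than 50% or to less than 30 ml/min, rash) requires stopping the co-trimoxazole". Leukopenia and hyperkalemia stand in the same list of examples.

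The early laboratory schedule is stated consistently:

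- **Week 1 (± 3 days), co-trimoxazole patients.** Section 8.1: "Blood drawn for electrolytes". Appendix A, footnote 2: "For subjects receiving co-trimoxazole, a blood sample to document electrolytes will be drawn at week 1, Visit 1A". The Safety Labs list in Appendix B gives the content: "Electrolytes: Sodium, Potassium, Chloride, Carbon Dioxide".
- **Month 1.** "Approximately 1 month (visit window of 1 month +/- 7 days) after enrollment, all subjects will be contacted by the site coordinator" (Section 8.2). This is a phone contact with no laboratory test.
- **Month 3.** "Approximately 3 months (visit window of 3 months +/- 7 days) after enrollment", the antimicrobial arm has chemistry, liver tests and CBC (Section 8.3). The Chemistry list in Appendix B is the one that contains "Urea Nitrogen (BUN) and Creatinine".

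Appendix A requires a new chemistry panel at enrollment only if none is available from the previous 90 days. Section 7.3 has patients start the drug without delay after randomization.

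**The concern.** The GFR trigger leads to a mandatory action, yet for roughly the first three months on drug the protocol schedules nothing that would show whether it has been met. A patient could enter just above 30 ml/min on an old panel and already be below it at the first dose, because the entry threshold and the absolute stop threshold are the same. Another patient's GFR could fall in the first days of treatment. In both cases the week-1 sample returns a potassium but no GFR.

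Patient safety is what is at stake. Section 5.3 names renal insufficiency with hypoaldosteronism, together with higher trimethoprim dose, as major risk factors for trimethoprim-related hyperkalemia. It relies on the eligibility criteria and on early monitoring to contain the risk. The eligibility check may rest on a value up to 90 days old, and the early monitoring does not include renal function. A non-serious renal decline is also not among the five adverse events of special interest in Section 10.4.

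**Working it through.** There is no sample-size, power or alpha figure to reproduce. The check compares the rule with the schedule and adds up the visit windows.

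**Can GFR be obtained at each contact?** Section 5 says that GFR is estimated from BUN and creatinine.

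| Contact | BUN and creatinine scheduled? | Source |
|---|---|---|
| Enrollment | Yes, but may be up to 90 days old | Appendix A |
| Week 1 ± 3 days | No (Na, K, Cl, CO2) | 8.1, Appendices A and B |
| Month 1 ± 7 days | No (phone) | 8.2, Appendix A |
| Month 3 ± 7 days | Yes | 8.3, Appendices A and B |

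Scheduled GFR values after enrollment and before month 3: zero.

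**Time on drug before the first scheduled GFR.** Take 3 months as 91 days and assume that the drug starts at enrollment.

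- Earliest: 91 − 7 = 84 days.
- Latest: 91 + 7 = 98 days.

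**Longest interval between two scheduled GFR values.** Oldest permitted panel plus latest month-3 visit: 90 + 98 = 188 days. Up to 90 of these days come before any drug is taken, so exposure without a scheduled GFR remains 84 to 98 days.

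**With BUN and creatinine added at week 1.**

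- First on-treatment GFR: 7 − 3 = day 4 to 7 + 3 = day 10.
- Gain: from 84 − 10 = 74 days to 98 − 4 = 94 days earlier.
- Interval that remains between the week-1 and month-3 values: the same 74 to 94 days.

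**Number of patients.** The documents give neither the share of the antimicrobial arm expected to start co-trimoxazole nor the frequency of an early GFR fall. No count can be derived.

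**The case against.** The strongest reply is that this is a choice about monitoring intensity. Section 5 leaves the definition of intolerance to the investigator and offers the GFR fall as one example. It says what to do when such a finding becomes known and does not promise a test by a given day. Leukopenia is in the same list, and the first scheduled on-treatment CBC is also at month 3, so the list was not built around the week-1 draw. This stands: a reader might infer that the protocol contradicts itself, and it does not.

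Second, the early concern stated in Section 5.3 is hyperkalemia, and week-1 potassium measures it directly. This also stands, and it rules out the inference that early hyperkalemia goes unmonitored. It does not close the gap, because Section 5 lists the GFR fall separately from hyperkalemia and a normal potassium at one time point says nothing about whether GFR has halved.

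Third, other safeguards exist. Patients with known GFR below 30, raised potassium or interacting drugs receive doxycycline. The month-1 call asks about problems with the drug. Follow-up is on a usual-care basis, the treating physician's safety judgment takes priority, and a medical monitor can be consulted. Some patients will therefore have an unscheduled creatinine. None of these supplies a scheduled value for the GFR trigger, however, although blood is already being drawn at week 1.

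Fourth, a week-1 creatinine catches only early falls or an outdated baseline. That is correct and limits what the change can achieve.

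**Conclusion.** The concern holds in a limited form. Between enrollment and about day 84 to 98 on co-trimoxazole, the protocol schedules no measurement from which the Section 5 GFR trigger could be assessed. This follows from the stated laboratory lists, which agree across Section 8.1 and both appendices. The day counts assume a 91-day three months and drug start at enrollment.

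Two further inferences are not supported. The 188-day maximum could be read as time on drug without a renal check, but up to 90 of those days precede treatment. A reader might also look for bias in the comparison of arms, but the point changes no estimate, test or power figure. Nor do the documents show that any patient would be harmed.

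This is an inexpensive patient-safety improvement that should be made, not a flaw that undermines the trial. Because the addendum to the SAP records that the trial was terminated early, the point now concerns the plan as written and any reuse of this monitoring schedule.

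**What to change.** In Section 8.1, Appendix A footnote 2 (with its table row) and Appendix B, replace the Electrolytes list with the existing Chemistry list at week 1 for co-trimoxazole patients. This keeps sodium, potassium, chloride and CO2 and adds BUN and creatinine. State that GFR is to be compared with the enrollment panel and the Section 5 rule applied. Because that rule requires stopping, add that a prompt repeat creatinine is taken where the investigator doubts that the rise reflects true loss of GFR.

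The cost is two analytes on a draw that already takes place, with no new visit. Appendix B allots 6 ml at week 1, against 8.5 ml at month 3 for CBC, chemistry and liver tests together. The downside is a few repeat tests or switches to doxycycline. Falls that begin after week 1 would still first be seen at month 3 unless usual care detects them.

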## I. Overview

---

CleanUP-IPF is a randomized, unblinded, multi-center clinical trial of patients with a diagnosis of idiopathic pulmonary fibrosis (IPF). A total of approximately 500 patients will be enrolled in the trial. Eligible patients will be randomized to the following treatment strategies:

- Standard care
- Standard care + oral antimicrobial therapy

Patients randomized to receive antimicrobial therapy will be given co-trimoxazole unless they have an allergy, contraindication to co-trimoxazole, renal insufficiency (GFR < 30 ml), are hyperkalemic (potassium > 5 mEq/L), or are concomitantly taking an angiotensin converting enzyme inhibitor (ACEI), angiotensin receptor blocker (ARB), or potassium sparing diuretic in which case they will receive doxycycline.

## II. Study Design

---

### **Randomization**

Eligible patients will be randomized 1:1 to either receive or not receive a prescription drug voucher for oral antimicrobial therapy in the form of one double strength 160mg trimethoprim/800mg sulfamethoxazole (double strength co-trimoxazole) twice daily plus folic acid 5 mg daily OR doxycycline 100mg once daily if weight < 50 kilograms or 100mg twice daily if weight > 50 kilograms.

### **Data Sources**

A database of case report form and biomarker core lab data will be created in eClinicalOS (eCOS), and the data then transferred to SAS for analysis. The randomized treatment assignment will be provided through data collected by the eCOS system.

## III. Analysis Population and Missing Data

---

The primary analysis will be based on intention to treat. All randomized patients will be included in the analysis population for assessing the primary and secondary endpoints. Extensive efforts being made in connection with the clinical sites to ensure data quality and completeness, it is expected that exclusion of patients for any endpoint analysis will be minimal.

For the primary endpoint patients without any observed non-elective, respiratory hospitalization or all-cause mortality will be censored at their last visit or lung transplantation. For the adjustment variables in the primary model the imputation method will be dictated by the amount of missingness. If all the adjustment variables

have a missing data rate of 2% or below (approximately 10 or less out of 500) then a simple imputation method will be implemented. If any one of the adjustment variables has a missing data rate over 2% (approximately more than 10 out of 500) then multiple imputation method will be implemented. For the simple approach categorical adjustment variables will be imputed to the mode and continuous adjustment variables will be imputed to the median value. For the multiple imputation the full conditional specification method (FCS) method will be used and assume an arbitrary missing data pattern [Berglund and Heeringa 2014]. The multiple imputation scenario (20 planned iterations) will be constructed which includes the treatment group indicator variable and the adjustment variables planned for the primary model.

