## IV. General Methodology

---

Definition of Statistical Significance: The statistical plan will test non-directional hypotheses, i.e., all tests will be 2-sided. The level of significance for all efficacy and safety analyses will be 0.05.

Statistical Tests: For situations where one observation per patient is observed, (e.g. safety comparisons at individual time points), a general analysis convention will be used unless otherwise specified. For continuous and ordinal variables, treatment group differences will be tested using the Wilcoxon rank-sum test for two groups and Kruskal-Wallis one-way analysis of variance for comparisons of more than two groups. For censored data, like time to event, treatment group differences will be tested using the log rank test. For discrete variables, treatment group differences will be tested using the chi-square test. In the situation of low cell counts the treatment group differences will be tested using Fisher's exact method.

Descriptive Statistics: For continuous and ordinal variables the number of observations, number of missing values, mean, standard deviation, median, twenty-fifth percentile, and seventy-fifth percentile will be given. For binary (e.g. yes/no), categorical, and/or ordinal variables a simple count and percent will be provided. Other statistics may be considered if necessary.

Descriptive Plots: Descriptive plots may be produced in addition to descriptive statistics if deemed appropriate. If deemed necessary plots of descriptive statistics such as spaghetti, mosaic, box, cumulative distribution, and loess curves will be provided.

Study Listings: Study data will be listed by treatment group, visit if applicable, and patient where appropriate.

Software and Validation Procedures: All data presented in interim and final analyses will be generated and validated under the guidance of the DCRI Clinical Trials Statistical SOPs.

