### **Primary Endpoint**

Endpoint Description: Time to first non-elective, respiratory hospitalization or all-cause mortality.

Response Variable Definition: Time to first respiratory hospitalization or all-cause mortality (primary endpoint) will be defined as the time to first observed event respiratory hospitalization or all-cause mortality. All patients will have some information regarding mortality and last visit of follow-up. Patients without any observed respiratory hospitalization or death event at the time of analysis will be censored at their last visit or lung transplantation. The respiratory hospitalizations will be reviewed and adjudicated by a clinical events committee (CEC).

Additional Covariates: Age, sex, baseline DLCO, baseline FVC, use of NAC at enrollment, use of standard of care medications at enrollment, and choice of antimicrobial agent prior to randomization. Note that the baseline DLCO and baseline FVC will be added to regression models using the % predicted versions for all endpoints.

Handling of Dropouts and Missing Data:

The censoring mechanism is assumed to be non-informative. Supportive analyses will be performed to assess the impact of a potential informative censoring.

Diagnostic tests: The additional continuous covariates to be used in the primary analysis model will be assessed for major departures from linearity by inspection of restricted cubic spline plots. If a departure is observed then a suitable transformation

will be explored. In addition the proportional hazard assumptions will be explored by inspection of Martingale residuals plots for all model covariates. If a major departure is observed then the variable will added to the model as a stratification variable.

Statistical Tests: The Cox proportional hazards regression model will be used to estimate outcome differences between the two treatment arms: “Standard care + oral antimicrobial therapy” and “Standard care”. The outcome is the time to first non-elective, respiratory hospitalization or all-cause mortality with model terms for treatment arm, baseline measurement, and covariates. Hazard ratios and 95% confidence intervals will summarize the differences between treatment arms.

Interpretation of Results: For Cox regression models a hazard ratio below 1.00 will indicate a reduction in events for “Standard care + oral antimicrobial therapy” arm. A hazard ratio above 1.00 will indicate increase in events for “Standard care + oral antimicrobial therapy” arm.

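### Above 2% missing, the SAP's imputation model for baseline covariates does not use the primary outcome, which loses part of the gain from adjustment; the effect on the treatment hazard ratio is small

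*SAP*

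**What the plan says.** SAP section III sets out two routes for missing adjustment variables in the primary model.

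- **All variables at 2% missing or below:** single imputation, in which "categorical adjustment variables will be imputed to the mode and continuous adjustment variables will be imputed to the median value".
- **Otherwise** ("If any one of the adjustment variables has a missing data rate over 2" per cent, roughly more than 10 of 500 patients): multiple imputation, for which "the full conditional specification method (FCS) method will be used and assume an arbitrary missing data pattern". The SAP adds that "The multiple imputation scenario (20 planned iterations) will be constructed", with a model that "includes the treatment group indicator variable and the adjustment variables planned for the primary model".

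That is the SAP's only description of the imputation model. Event status, survival time and cumulative hazard do not appear in it, and the May 2020 addendum leaves the imputation unchanged.

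The completed data feed the primary analysis: "The Cox proportional hazards regression model will be used to estimate outcome differences between the two treatment arms". Its covariates are "Age, sex, baseline DLCO, baseline FVC, use of NAC at enrollment, use of standard of care medications at enrollment" and the antimicrobial agent chosen before randomization. The documents give no expected rate of missing covariate data.

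**The concern.** An imputation model should preserve the associations that the analysis model estimates. If DLCO is imputed from treatment and the other covariates alone, the imputed values have no further relation to the outcome, although baseline lung function is in the Cox model because it is expected to predict hospitalization and death.

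Two consequences follow. The coefficient of the imputed covariate shrinks. The adjustment is also weaker, so a non-null adjusted treatment hazard ratio drifts toward the unadjusted one, which lies nearer 1. What is at stake is some of the benefit of a prespecified adjusted primary analysis.

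**Working it through.** **1. The plan's own figures.** Protocol 11.3, Table 1, gives 93% power for 12-month event rates of 30% and 20.0% with 500 patients.
- Implied hazard ratio under exponential times: ln(0.80)/ln(0.70) = 0.6256.
- Uniform 30-month accrual, 12-42 months of follow-up and 2% per year dropout give 226 expected events.
- Schoenfeld: z = (√226/2) × |ln 0.6256| − 1.96 = 3.53 − 1.96 = 1.57, power 94.1%.
- Freedman: z = √226 × (1 − 0.6256)/(1 + 0.6256) − 1.96 = 3.46 − 1.96 = 1.50, power 93.4%.

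The design is reproduced. All nine rows of Table 1 agree within 2 points and all 18 cells of Table 2 within one event. The point disputes none of these figures; they set the simulation.

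**2. What the imputation should condition on.** Under a Cox model with treatment T, observed covariates Z, missing covariate X, event indicator D and time t,

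log p(X | Z, T, t, D) = const + log p(X | Z, T) + D·γX − H0(t)·exp(βT + γX + δZ).

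The SAP's list supplies only p(X | Z, T). The omitted terms depend on D and the cumulative hazard H0(t), which is why the event indicator and the Nelson-Aalen estimate are the natural additions.

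A rough guide comes from the linear-model analogue. A fraction m of the values has no residual covariance with the outcome, so the coefficient becomes about (1 − m)γ. Expected attenuation is then about 3, 5, 10 and 20% at those missing rates.

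**3. Simulation.** 500 replicates, n = 500, 1:1, conditional hazard ratio 0.6256, control 12-month rate 30%, accrual and dropout as in 11.3, follow-up capped at 36 months (protocol section 8), 20 imputations.

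Assumptions not taken from the documents:
- DLCO missing completely at random in 3, 5, 10 or 20%, with half of those patients also missing FVC.
- DLCO-FVC correlation 0.5.
- Log hazard ratios per SD (DLCO/FVC) of −0.5/−0.3 (moderate) or −0.8/−0.5 (strong).

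DLCO coefficient:

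| Effects | Complete data | Missing | Outcome not used | Attenuation | Outcome used |
|---|---|---|---|---|---|
| Moderate | −0.512 | 3% | −0.493 | 4% | −0.510 |
| | | 5% | −0.480 | 6% | −0.508 |
| | | 10% | −0.451 | 12% | −0.505 |
| | | 20% | −0.394 | 23% | −0.501 |
| Strong | −0.815 | 3% | −0.778 | 5% | −0.810 |
| | | 5% | −0.753 | 8% | −0.805 |
| | | 10% | −0.698 | 14% | −0.796 |
| | | 20% | −0.596 | 27% | −0.780 |

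For example, 1 − 0.451/0.512 = 12%, close to the rough guide.

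Treatment hazard ratio:

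| Effects | Complete data | Missing | Outcome not used | Outcome used |
|---|---|---|---|---|
| Moderate | 0.628 | 3% | 0.630 | 0.629 |
| | | 5% | 0.632 | 0.630 |
| | | 10% | 0.635 | 0.630 |
| | | 20% | 0.641 | 0.633 |
| Strong | 0.621 | 3% | 0.627 | 0.623 |
| | | 5% | 0.631 | 0.624 |
| | | 10% | 0.638 | 0.627 |
| | | 20% | 0.652 | 0.632 |

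- The unadjusted hazard ratios are 0.674 (moderate) and 0.708 (strong), so the drift is toward the unadjusted value.
- Moderate shifts in the log hazard ratio are 0.0035 to 0.0209, with Monte Carlo standard errors of 0.0005 to 0.0015. The direction is not noise.
- Against a treatment standard error of about 0.14-0.15, the shift is 0.02-0.15 standard errors (moderate) or 0.06-0.32 (strong).
- The part due to leaving out the outcome, at 3-10% missing, is 0.0015-0.005 (moderate) or 0.004-0.011 (strong) on the hazard ratio. The rest remains with the outcome included.
- Simulated power, moderate: 91.8, 91.0, 90.0 and 88.6% against 92.0% with complete data. The Monte Carlo standard error is 1-2 points, so this is only indicative.
- **True hazard ratio 1, 10% missing:** log hazard ratio shifts of 0.0005 and 0.0018 (Monte Carlo standard errors 0.0010 and 0.0016), with rejection in 5.2% and 3.2% of trials.
- At 5-20% missing, median imputation moved the hazard ratio less than imputation without the outcome (10% missing: 0.631 against 0.635 moderate, 0.628 against 0.638 strong).

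**The case against.** The case for leaving the plan alone has real force.

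- **The larger percentages concern a nuisance parameter.** SAP mock-up Table 3.2 reports the treatment hazard ratio and no covariate coefficients. This stands: at 3-10% missing the effect on the reported result is a small fraction of a standard error.
- **The planned power never relied on adjustment.** Protocol 11.3 uses an unadjusted log-rank test. This stands: what is lost is extra gain, not power that the design claimed.
- **The rule may never be triggered.** Protocol 7.2 requires spirometry and DLCO before randomization if no recent result exists, and age, sex and medications are recorded then. This stands: missingness may be low, and the larger shifts come from the top of an assumed range.
- **The list may not be exhaustive.** To say that the model includes certain variables does not strictly rule out others, so a reader who infers deliberate exclusion of the outcome goes beyond the text. But no other description exists, and an analyst following it would omit the outcome. If it was meant to be included, the SAP should say so.

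Three stronger readings are tempting and unsupported. One is that the primary test is biased or invalid: randomization protects it, and the simulations under the null show neither a shift nor excess rejections. Another is that the estimate always moves in one direction: that applies only to a non-null effect, and the movement reflects weaker adjustment. The third is that the same defect affects the secondary endpoints: section III specifies imputation only for the adjustment variables of the primary model.

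**Conclusion.** The point holds as a minor specification weakness in the primary analysis. Once the 2% threshold is passed, the imputation model as described weakens covariate adjustment appreciably only when much of DLCO or FVC is missing, and moves a non-null treatment hazard ratio in the third decimal place at 3-10% missing with moderate covariate effects. The largest shift found, 0.621 to 0.652, needs 20% missing and strong effects, and about a third of it remains with the outcome in the model (0.621 to 0.632). In these simulations, passing the threshold also replaces median imputation with a method that moved the treatment hazard ratio more.

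The direction follows from the structure of the two models. The sizes rest on assumed missing rates, a completely random mechanism, and assumed covariate effects and correlation. They also assume the full planned design, whereas the addendum records early closure and gives no final event count.

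**What to change.** For the primary Cox analysis, state in SAP section III that the imputation model contains treatment, all adjustment variables, the primary event indicator, and the Nelson-Aalen cumulative hazard at each patient's event or censoring time. Event and time should be those of the primary analysis, including censoring at lung transplantation and the addendum's rule for unadjudicated events.

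The cost is two extra variables and one sentence. The crossover-censored analysis and the addendum's two cut-off analyses redefine event and time, so a further clause should say whether they reuse the primary imputations or repeat them with their own outcome. If the primary analysis has already been run and the threshold was passed, report the revised imputation as a sensitivity analysis. If no adjustment variable exceeded 2% missing, nothing need be rerun.
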